2.27 Follow-Up Evaluations

The subject will have a phone visit specific to the study at 7 days (+/- 3 days) and follow-up clinic visits at 1 month (+/- 5 days), at 3 months (+/- 10 days), at 6 months (+/- 30 days), at 12 months (+/- 60 days), at 24 months (+/- 60 days), at 36 months (+/- 60 days), at 48 months (+/- 60 days, phone call), and at 60 months (+/- 60 days). At each clinic visit, the subject will undergo medical evaluation, completion of symptom scores, uroflow and assessment of adverse events. The 60-month visit is the final visit. The **blinded team** is responsible for 7 days through 36 months follow up activities. Forty-eight (48) and 60 months follow up activities can be performed by **either the blinded or the unblinded team**.

2.28 Competing Studies

In the event where a study center is participating in similar and competing research studies with the same or similar subject populations, the Investigator must provide documentation on the methods the center is using to minimize selection bias when allocating subjects for the WATER Study.

2.29 Study Assessments

The schedule of assessments is shown in **Table 2**. Details of selected assessments are provided below:

Table 2. Schedule of Assessments

Evaluation	Baseline w/in 90 days of Tx	Tx	Post-Op	Follow-Up Clinic Visits						
				1 wk (+/-3 days) (phone)	1 mon (+/-5 days)	3 mon (+/-10 days)	6 mon (+/-30 days)	12,24,36 mon (+/- 60 days)	48 mon (+/- 60 days)(pho ne)	60 mon (+/- 60 days)
Medical history	X									
Vital Signs /Urological Examination	X				X ⁷ (vital signs only)					
PSA	X						X	X		X
Serum Blood Test for CBC and electrolytes	X		X ⁴							
Urine for M/C/S	X	X ¹								
Qmax and PVR	X				X	X	X	X		X
Cystourethroscopy	X (within 3 months)	X ²								
Urodynamics (at selected sites)	X (within 6 months)						X			
Pain NRS and Dysuria Score		X ³	X ⁵	X	X	X				
Incontinence Severity Index	X		X ⁵	X	X	X	X			
Blinding Questionnaire			X	X	X	X	X	X		
IPSS, EQ-5D, IIEF-15, MSHQ-EjD, WPAI:US	X			X	X	X	X	X	X ⁶	X ⁶
TRUS	X (within 6 months)	X				X				
DRE	X					X				
Concomitant Medication	X	X	X	X	X	X	X	X	X ⁸	X ⁸
Concomitant Procedure			X	X	X	X	X	X		
Procedure information		X								
Adverse events		X	X	X	X	X	X	X	X ⁹	X ⁹

¹ Urine dipstick analysis to be done within 72 hours prior to procedure

² Rigid cystoscopy is required

³ To be assessed immediately prior to the procedure

⁴ Done in the recovery room

⁵ To be completed post-catheter removal

⁶ IPSS, IIEF15, and MSHQ-EjD only

⁷ If subject has intraoperative or postoperative cardiovascular event

⁸ Only urological adverse events related medication and all BPH medication

⁹ Only urological adverse events

Medical history. During the baseline assessment, the investigator or coordinator will record details of medical history as they relate to BPH.

Vital Signs / Urological examination. At baseline the investigator will measure vital signs and perform a focused urological examination and document any preoperative abnormalities. Vital signs will be collected at the 1-month visit if the subject had an intraoperative or post-operative cardiovascular adverse event.

Serum Blood Test. A blood sample will be collected to measure PSA, complete blood count (CBC) and electrolytes (to include at least levels of sodium, blood urea nitrogen and creatinine). Test timing is shown in the schedule of assessments.

Urine for M/C/S. A mid-stream urine sample will be collected at baseline, and repeated within 72 hours prior to the procedure to exclude current urinary tract infection.

DRE. Digital rectal examination (DRE) will be performed to assess the prostate for size and the presence of nodular or hard tissue.

TRUS. Transrectal ultrasound (TRUS) shall be performed to assess eligibility for prostate volume, length, transverse width, anterior/posterior width and general condition of the prostate. Presence of a middle or intravesical lobe should be documented by sagittal images. The investigator will estimate prostate volume using standard methods ($\text{length} \times \text{width} \times \text{height} \times \pi/6$).

Uroflow. At baseline and each follow-up visit, the subject will undergo measurement of urinary flow rate (Qmax) and post-void residual volume (PVR). For Qmax to be valid for a patient, the total voided volume must be $\geq 125\text{mL}$. If the total voided volume is less than 125mL , the voided volume must be equal to or greater than 50% of the bladder capacity (defined as voided volume + PVR). The subject can repeat the test if necessary.

Urodynamics. Detrusor pressure (PDet@Qmax) will be measured at selected sites. Sites should follow the methods outlined in Chapple [14].

Cystoscopy. At baseline, cystoscopic examination will be performed to assess the bladder for presence of cancer, trabeculation and positioning of the ureteric orifices and the urethra for evidence of stricture (including bladder neck contracture) and prostatic lobe formation (both lateral and medial). Baseline historical cystoscopy will be accepted if the following 2 conditions are met: 1) Baseline cystoscopy was performed and recorded by the study investigator(s) within 90 days of treatment, and 2) The cystoscopy report includes sufficient information for the monitor to source verify all the related inclusion/exclusion criteria, including findings on the area of the bladder neck.

Blinding Questionnaire. A method of assessing subjects knowledge of procedure awareness.

Pain Severity Assessment (NRS) and Dysuria Score. A method of measuring post-operative pain and pain on micturition.

International Prostate Symptom Score (IPSS). IPSS is a validated measure of urinary dysfunction due to BPH [14]. Subjects will complete an IPSS form at baseline and at each follow-up visit.

EuroQol Group 5-Dimension Self-Report Questionnaire (EQ-5D). EQ-5D [15] is a validated instrument that measures health-related quality of life in five dimensions: mobility, self-care, usual activities, pain/discomfort, and anxiety/depression. It also includes the EQ-VAS which is used to measure the individual's global self-rated health status. Subjects will complete an EQ-5D form at baseline and at each follow-up visit up to 36 months.

International Index of Erectile Function Questionnaire (IIEF-15). IIEF-15 [16] is a validated, fifteen-item questionnaire designed to diagnose the presence and severity of erectile dysfunction. Subjects will complete an IIEF-15 form at baseline and at each follow-up visit up to 60 months.

Male Sexual Health Questionnaire to assess Ejaculatory Dysfunction (MSHQ-EjD). MSHQ-EjD [17] is a validated, four-item questionnaire that assesses ejaculatory function and related distress or bother. Subjects will complete a MSHQ-EjD form at baseline and at each clinic visit up to 60 months.

Incontinence Severity Index (ISI). ISI [18] is a validated means of assessing incontinence and will assist in isolating *de novo* incontinence rather than preexisting incontinence secondary to Bladder Outlet Obstruction.

WPAI: US: is a validated six-item questionnaire that assess the effect of urinary symptoms on a subject's ability to work and perform regular activities.

Concomitant Medications. All medications will be recorded on a rolling log up to 36 months follow-up visit. All urological AE related medication and BPH related medication will be recorded for 48 and 60 months follow-up phone call/visit.

Concomitant Procedures. All urologic procedures that occur during follow-up will be recorded on a rolling log up to 36 months follow-up visit.

2.30 Adverse events.

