[†]This includes the following: persistent ejaculatory dysfunction, erectile dysfunction or urinary incontinence and urinary retention requiring re-catheterization after 3 days post-procedure. Note that bladder catheterization itself is considered a Clavien-Dindo Grade 1 event.

2.30.2 48 & 60 months AE collection

For the 48-month phone call and 60-month follow-up visit, only urological adverse event data will be recorded in the study-specific Electronic Data Capturing system. Study investigators have the responsibility to report all type of AEs to the respective IRB/IEC per each institution's requirement.

AE information (start and stop date, description of event, and severity) will be assessed and recorded on CRFs. Events that meet the criteria of an SAE in **Table 3** must be reported to the Sponsor within 24 hours of the site's awareness.

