3.3 Additional Endpoint Assessments (already reported)

The following is a list of secondary endpoints intended to support product labeling. Statistical details are provided in another section.

- Reoperation or re-intervention within 6 months. Reoperation means any surgical procedure on the lower urinary tract to treat problems potentially related to BPH. Re-intervention means any invasive procedure (e.g., cystoscopy) to evaluate problems potentially related to BPH. Re-intervention excludes TRUS and urodynamics evaluations required by the study during follow-up.
- Evaluation of the proportion of sexually active subjects reporting a worsening of sexual function through 6 months on either the IIEF-15 or the MSHQ-EjD questionnaires
- Evaluation of the proportion of subjects meeting a composite of serious device or procedure related events defined as MAUE through 6 months
- Length of hospital stay (days) in the treatment groups
- Length of operative time (minutes) in the treatment groups, defined as time from pre-treatment visualization to insertion of indwelling catheter (IDC).
- Length of resection time (minutes) in the treatment groups, defined as start of first pedal activation to end of last pedal use for either Aquablation or TURP.

The following objectives are pre-specified but are not intended to support product labeling:

- Evaluation of proportion of subjects with Clavien-Dindo classification of Grade 2 or higher or any Grade 1 with persistent disability (e.g. ejaculatory disorder or erectile dysfunction) at 30 days, 6 months, and 1 year
- Evaluation of the proportion of subjects with Dysuria through 30 days
- Duration of catheterization (hours)
- Change in hemoglobin (gm/dl) at discharge from baseline
- Reoperation or Re-intervention within 30 days, 12 months, 24 months 36 months, 48 months, and 60 months
- Changes in the proportion of subjects using medications for BPH symptoms at month 6. An additional analysis of change in total daily dose of BPH-specific medications (e.g., alpha blockers, prostaglandin inhibitors, phosphodiesterase inhibitors, etc.) at month 6 will be performed.
- IPSS score at baseline, and 7 days, 1, 3, 6, 12, 24, 36 months, 48 months, and 60 months
- IPSS-QoL at baseline, and 7 days, 1, 3, 6, 12, 24, 36 months, 48 months, and 60 months
- Qmax at baseline, 1, 3, 6, 12, 24, 36 months and 60 months
- PVR at baseline, 1, 3, 6, 12, 24, 36 months and 60 months
- Outcome of device/procedure related serious adverse events

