## 7 Additional Endpoint Assessments

The following additional endpoints, evaluated using the PP cohort, are pre-specified but are not intended to support product labeling. Comparisons of proportions described below will be done using methods similar to those described for the reoperation/reintervention secondary endpoint. Comparisons of continuous variables will use a t test unless otherwise described. Testing of continuous variables will examine superiority, and in some cases, non-inferiority. Superiority tests will be 2-sided ( $\alpha=0.05$ ). Non-inferiority tests will be one-sided ( $\alpha=0.025$ ).

1. Proportion of subjects with Clavien-Dindo classification of Grade 2 or higher or any Grade 1 with persistent disability (e.g. ejaculatory disorder or erectile dysfunction) at 30 days, 6 months, and 1 year. 6-month and 1-year calculations will be performed only when full datasets are available. A 10% NIM will be used.

---

\* According to personal communication [name], creator of MSHQ, no published MCID for MSHQ exists.

2. Evaluation of the proportion of subjects with dysuria through the day 30 visit. Dysuria is defined as burning sensation while urinating of at least “about ½ the time” on the dysuria questionnaire. An additional comparison using proportion odds logistic regression will be performed. A 15% NIM will be used.
3. Duration of bladder catheterization (i.e., intraoperative catheter placement to removal prior to discharge) after the assigned study procedure. Duration will be compared with a t test. An NIM of ½ a day will be used.
4. Change in hemoglobin (gm/dl) (i.e., laboratory test) at discharge from baseline.
5. Reoperation or Re-intervention within 30 days, 12 months, 24 months and 36 months. For the 30-day time point, proportions will be compared with a 10% NIM. For longer time points, due to the expectation of study withdrawal, Kaplan-Meier survival analysis will be performed and a log rank test calculated.
6. Changes in the proportion of subjects using medications for BPH symptoms at month 6. Two analyses will be done. 1) an analysis of the proportion of subjects who increased doses of BPH medications or started a new BPH medication, and 2) the proportion who were able to decrease or stop doses of BPH medications. Relevant medications include alpha blockers, prostaglandin inhibitors, and phosphodiesterase inhibitors. A 10% NIM will be used.

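### Reoperation or re-intervention is an endpoint at 48 and 60 months, but the urologic-procedure log ends at 36 months, so late retreatment could be undercounted

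*Protocol*

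**What the plan says.** **Endpoint.** Protocol section 3.3 includes, among the objectives that are pre-specified but not for labeling: "Reoperation or Re-intervention within 30 days, 12 months, 24 months 36 months, 48 months, and 60 months". The definitions, given earlier in that section, are broad. The first covers surgery: "Reoperation means any surgical procedure on the lower urinary tract to treat problems potentially related to BPH". The second reaches beyond treatment to invasive diagnostic work: "Re-intervention means any invasive procedure (e.g., cystoscopy) to evaluate problems potentially related to BPH". A diagnostic cystoscopy prompted by possible BPH problems therefore counts.

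**Procedure collection.** Protocol section 2.29 says: "All urologic procedures that occur during follow-up will be recorded on a rolling log up to 36 months follow-up visit". Table 2 agrees: the concomitant-procedure row is marked through the 12, 24 and 36 month column and is blank at 48 and 60 months.

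**Medication, for contrast.** The full medication log also ends at 36 months, but section 2.29 continues it in reduced form: "All urological AE related medication and BPH related medication will be recorded for 48 and 60 months follow-up phone call/visit". Procedures have no such sentence.

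**Adverse events.** At the two late contacts, section 2.30.2 says "only urological adverse event data will be recorded in the study-specific Electronic Data Capturing system", and Table 2 footnote 9 reads "Only urological adverse events". The fields named are start and stop date, description and severity. Serious events must still reach the sponsor within 24 hours.

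**Analysis.** SAP section 7 item 5 covers "Reoperation or Re-intervention within 30 days, 12 months, 24 months and 36 months", with Kaplan-Meier and a log rank test for the time points after 30 days. It plans nothing for this endpoint at 48 or 60 months.

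**The concern.** The endpoint was extended to five years and its source data were not. A site that follows section 2.29 and Table 2 exactly would close the procedure log at the 36-month visit and need not ask about procedures afterwards. The only remaining route is a record designed for something else.

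The protocol summary gives long-term data as the reason for following randomized and treated men to five years, and this is the listed endpoint that measures retreatment directly. If late procedures are incompletely recorded, the 48- and 60-month proportions will be too low by an unknown amount. It will also be harder to identify retreated men when reading the 48- and 60-month IPSS or the 60-month Qmax and PVR. Procedures not asked about at the time would have to be reconstructed later from recall or from records that the study did not collect.

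**Working it through.** The documents give no 48- or 60-month retreatment rate, so there is no figure to reproduce. The check sets the endpoint beside its data source and then shows what the size of the problem depends on.

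**1. Share of each window without the log** (endpoint times from protocol 3.3, end of log from 2.29)

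- 60-month endpoint: (60 − 36)/60 = 24/60 = 40%.
- 48-month endpoint: (48 − 36)/48 = 12/48 = 25%.

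**2. What the adverse event route can catch**

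- Surgery for a complication, or with an unplanned admission: probably caught, as a urological adverse event or a serious adverse event.
- Elective surgery for returning symptoms: uncertain. Table 3 excludes planned hospitalization for a pre-existing condition without serious deterioration from the serious category, and section 2.30.2 names no procedure field.
- Diagnostic cystoscopy: meets the endpoint definition but is not itself an untoward occurrence. It is caught only if someone records an event and mentions the procedure in the description.

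Other checks are lighter in this period. Month 48 is a phone call (2.27), monitoring at 48 and 60 months is remote (6.4), and the events committee's adjudication runs to 12 months (6.1).

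**3. Illustration of size**

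Assumptions, none from the documents: a constant annual retreatment hazard h of 1%, 2% or 3%, and a fraction c of retreatments in months 36 to 60 that is captured through adverse event records. No allowance is made for attrition. The cohort is the protocol's maximum of 181 men (2.11).

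- True 60-month risk = 1 − exp(−5h)
- Observed risk = [1 − exp(−3h)] + c × [exp(−3h) − exp(−5h)]
- Men missed = 181 × (true − observed)

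For h = 2% and c = 0: true = 1 − exp(−0.10) = 9.52%; observed = 1 − exp(−0.06) = 5.82%; missed = 181 × 0.0369 = 6.7 men, or 38.8% of those retreated.

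| h per year | true risk | c = 0: observed (men missed) | c = 0.5 | c = 0.9 | c = 1 |
|---|---|---|---|---|---|
| 1% | 4.9% | 3.0% (3.5) | 3.9% (1.7) | 4.7% (0.3) | 4.9% (0) |
| 2% | 9.5% | 5.8% (6.7) | 7.7% (3.3) | 9.2% (0.7) | 9.5% (0) |
| 3% | 13.9% | 8.6% (9.6) | 11.3% (4.8) | 13.4% (1.0) | 13.9% (0) |

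The share of retreated men missed is about 38-39% at c = 0, 19-20% at c = 0.5 and 4% at c = 0.9. It hardly depends on h; it depends on c. The c = 0 column is an upper limit, since some capture through adverse events is to be expected.

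**4. Effect on the comparison of arms**

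Let L_A and L_T be the true risks of late retreatment in the two arms, and c_A and c_T the captured fractions. The recorded late difference is c_A·L_A − c_T·L_T. If c_A = c_T = c, the absolute late difference shrinks by the factor c and the late ratio is unchanged. If the fractions differ, the error can go in either direction. The documents give neither fraction, and section 2.27 lets either the blinded or the unblinded team perform these contacts, so equal capture is not assured.

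**The case against.** The strongest reply is that retreatment does not vanish after month 36. Any untoward medical occurrence is an adverse event under Table 3, urological ones are still recorded with dates and a description, serious ones are still reported within 24 hours, and the 60-month contact is a clinic visit with medical evaluation. Section 2.26 treats invasive urologic management as care for an adverse event, and SAP section 6 describes reoperation or re-intervention as a component of the primary safety endpoint, which is built from adverse events. Most surgical reoperations may well be captured. This stands, and it narrows the gap to diagnostic procedures and to those not entered as, or described within, an adverse event.

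A reader might infer more: that nothing is captured after month 36, that the five-year rate will be undercounted, and that the arms will be drawn together so that a true late difference passes for equal durability. The documents do not support this. Capture through adverse events is neither excluded nor quantified, and the effect on the arm difference is undetermined. Nor do they say that retreatment lies outside adverse event recording because it reflects lack of effect: the Table 5 note concerns BPH medication and Grade 2, and the remark in section 3.1 concerns Clavien-Dindo grading.

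The SAP's stop at 36 months is not separate evidence of undercounting. The SAP cites protocol Version G and 2016 agency feedback, whereas the current protocol is Revision H of August 2020, so the SAP appears simply not to have been updated. There is as yet no planned five-year comparison to be biased.

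Finally, the endpoint is neither primary nor for labeling, and IPSS, Qmax, PVR and BPH medication also inform durability. That lowers the priority but does not supply the missing procedure data.

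**Conclusion.** The mismatch is established from the text and the table together: the endpoint runs to 60 months and the dedicated procedure record to 36, leaving 24 of 60 months (40%) uncovered. The endpoint could undercount retreatment. In the illustration, which assumes a constant 1-3% per year and no attrition, the shortfall in 181 men runs from none with full capture to 3.5-9.6 men with no capture. The documents do not place the trial within that range.

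Study success, type I error and power are unaffected. This is an inconsistency that should be fixed; it is not a threat to the trial's main conclusions.

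**What to change.** 1. **Protocol Table 2:** mark concomitant procedure at the 48-month call and the 60-month visit.
2. **Protocol section 2.29:** extend the procedure log to the 60-month visit, at least for lower urinary tract procedures including cystoscopy, with date and reason. Ask every subject, at both contacts, whether he has had such a procedure since the last contact.
3. **SAP section 7 item 5:** extend the Kaplan-Meier and log rank analysis to 48 and 60 months, censoring each man without an event at the last contact at which procedures were asked about. Men not asked after month 36 then do not count as event-free to month 60.

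The cost is a few minutes at two contacts that already take place, using a log that already exists, and one sentence in the SAP.

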2.30.1 AE collection up to 36 months

The occurrence of all adverse events will be documented in all study subjects from the study treatment visit through 36 months follow-up period.

AE information (start and stop date, description of event, severity, relatedness to the treatment procedure, the device itself or other study-related procedures) will be assessed and recorded on CRFs. Whether an AE meets the definition for serious adverse event will be determined by the study investigator and sponsor using the ISO 14155 definition (**Table 3**). All events consistent with an SAE must be reported to the Sponsor within 24 hours of awareness of the event. Relatedness of the AE to the surgical procedure or the study device itself will be judged by the investigator according to **Table 4**.

The classification of surgical complications shall be done per **Table 5**. Note that persistent ejaculatory or erectile dysfunction, the need for re-catheterization after postoperative day 3, and urinary incontinence related to surgery are considered to be surgical complications.

Table 3 Adverse event definitions (ISO 14155).

Term	Definition
Adverse event* (AE)	Any untoward medical occurrence, unintended disease, or injury, or untoward clinical signs in subjects, whether or not related to the investigational medical device
Serious adverse event* (SAE)	An adverse event that: 
 a). led to a death, b). led to a serious deterioration in the health of the subject that either resulted in 
 1). a life-threatening illness or injury, or 2). a permanent impairment of a body structure or a body function, or 3). in-patient or prolonged hospitalization, or 4). medical or surgical intervention to prevent life-threatening illness or injury or permanent impairment to a body structure or a body function NOTE: Planned hospitalization for a pre-existing condition, or a procedure required by the CIP, without serious deterioration, is not considered a serious adverse event.

Adverse device effect (ADE)	An adverse event related to the use of an investigational medical device. This term includes any event resulting from insufficient or inadequate instructions for use, operation, or any malfunction, any event resulting from use error or from intentional misuse of the investigational medical device
Serious adverse device effect (SADE)	An adverse device effect that has resulted in any of the consequences characteristic of a serious adverse event
Unanticipated Adverse Device Effect (UADE)	A serious adverse effect which by its nature, incidence, severity or outcome has not been identified in the current version of risk analysis report.

*Note that these definitions do not imply a relationship between the adverse event and the study device.

Table 4. Adverse event relatedness categories.

Term	Definition
Unrelated	No evidence that AE related to treatment procedure or device
Unlikely	While the AE could be due to a procedure or device, an alternative explanation is highly likely.
Possibly	AE is plausibly related to treatment procedure or device but an alternative explanation is more likely
Probably	AE likely to be related to treatment procedure or device even though alternative explanations are possible
Definitely	AE almost certainly related to treatment procedure or device

Table 5. Classification of surgical complications according to the modified Clavien-Dindo grading system [19].

Grade	Definition
Grade 1	Any deviation from the normal postoperative course without the need for pharmacological treatment or surgical, endoscopic and radiological interventions. Allowed therapeutic regimens are: drugs as antiemetics, antipyretics, analgetics, diuretics and electrolytes and physiotherapy. This grade also includes wound infections opened at the bedside. [†]
Grade 2	Requiring pharmacological treatment with drugs other than such allowed for grade I complications. Blood transfusions and total parenteral nutrition are also included.*
Grade 3	Requiring surgical, endoscopic or radiological intervention.
Grade 3a	Intervention not under general anesthesia.
Grade 3b	Intervention under general anesthesia.
Grade 4	Life-threatening complication (including CNS complications: brain haemorrhage, ischaemic stroke, subarachnoid bleeding, but excluding transient ischaemic attacks) requiring IC/ICU management.
Grade 4a	Single organ dysfunction (including dialysis).
Grade 4b	Multi-organ dysfunction.
Grade 5	Death of a subject.

*Note that the need for medications related to BPH (e.g., alpha blockers) is likely related to lack of effectiveness (not safety) and is not considered to meet criteria for a Grade 2 event.

[†]This includes the following: persistent ejaculatory dysfunction, erectile dysfunction or urinary incontinence and urinary retention requiring re-catheterization after 3 days post-procedure. Note that bladder catheterization itself is considered a Clavien-Dindo Grade 1 event.

2.30.2 48 & 60 months AE collection

For the 48-month phone call and 60-month follow-up visit, only urological adverse event data will be recorded in the study-specific Electronic Data Capturing system. Study investigators have the responsibility to report all type of AEs to the respective IRB/IEC per each institution's requirement.

AE information (start and stop date, description of event, and severity) will be assessed and recorded on CRFs. Events that meet the criteria of an SAE in **Table 3** must be reported to the Sponsor within 24 hours of the site's awareness.

